Official Title: Preliminary Studies to Test the Effects of Ambulatory Voice Biofeedback

NCT Number: 03416829

Date: June 16th, 2022

Study Protocol:

Study One will assess if AVB paradigms can effect short- and long-term changes in vocal loudness behavior in a small group of patients with vocal hyperfunction (VH). More specifically, it will determine which of three types of ambulatory feedback results in better learning/retention (100% frequency, 25% frequency, or delayed summary feedback every 2 minutes of voicing) of a new vocal behavior (reduced vocal loudness) in three groups of 15 patients with vocal fold nodules. It is hypothesized that patients receiving lower frequency or summary feedback will produce lower initial performance but higher short- and long-term retention than patients receiving feedback 100% of the time.

Inclusion/Exclusion criteria for the patients are summarized below:

Inclusion Criteria	Exclusion Criteria
Age: 18 – 65 years Previous monitoring: Patients must have successfully completed approximately 1 week of baseline voice monitoring in protocol 2011P002376 For Study 1 only: Diagnosis: vocal fold nodules	Non-English Speaker Unable to answer questions and/or follow instructions Patients with a sensitivity to hypoallergenic adhesive Pregnant women

Study One will include 54 total patients with phonotraumatic VH (45 patients + potential 20% dropout rate) and will be recruited from the Massachusetts General Hospital (MGH) Voice Center. The procedures and design for Study One are essentially identical to a previously approved IRB protocol (# 2014001870) which used normal subjects [37]. The proposed study seeks to replicate the previous results in patients with VH in order to move toward the clinical implementation of this approach. Each subject will be assigned (via block randomization) to three groups with different AVB schedules: 1) 100% immediate biofeedback (vibrotactile cueing every time the participant exceeds a vocal intensity threshold), 2) 25% immediate biofeedback (vibrotactile cueing every 4th time the participant exceeds a vocal intensity threshold), and 3) delayed summary biofeedback (no cueing; summary statistics shown every 2 minutes of voiced time). Patients with phonotraumatic VH have been chosen since reducing vocal loudness is often a goal of therapy.

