Study One will use a series of two 3 (Group) X 4 (Day - baseline, biofeedback, short- and long-term retention) mixed between/within ANOVAs will be conducted for the outcome variables Δ dB and overall percentage compliance. The findings of interest are the main effects of “Day” and the interaction effects of Group X Day. While appropriate post hoc tests will be conducted on the main effects (if significance is achieved), univariate follow-up tests, and if required, appropriate post hoc tests will be performed on the interaction effects. Results from our preliminary research [6] produced large effect sizes ($\eta^2 \approx 0.90$) between the biofeedback and non-biofeedback/baseline time periods. Furthermore, both limb and head/neck motor learning studies have demonstrated large effect sizes ($\eta^2 = 0.70-0.95$) between different feedback groups (decreasing frequency [10, 13-21, 49, 50] or delayed summary [10, 22-30, 51-53] feedback). Based on the

lower effect size ($\eta^2 = 0.70$) and the experimental design, power analysis indicated a sample of 14 participants per group with 80% power and alpha of 0.05. Since there are three experimental groups in Study One, the total sample size would need to be higher than 42 participants

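### The power calculation does not reproduce: eta-squared 0.70 at 80% power and alpha 0.05 needs 2 to 6 patients per group, not 14, and the effect detectable with 15 per group is not given

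*Combined protocol and SAP*

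**What the plan says.** The Statistical Analysis Plan describes the analysis as a "series of two 3 (Group) X 4 (Day - baseline, biofeedback, short- and long-term retention) mixed between/within ANOVAs", one for each of two outcomes. It names as findings of interest the Day main effects "and the interaction effects of Group X Day".

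For the design effect, it cites motor-learning studies with "large effect sizes ($\eta^2 = 0.70-0.95$) between different feedback groups" and takes the bottom of that range. From the "lower effect size ($\eta^2 = 0.70$) and the experimental design" it reports that "power analysis indicated a sample of 14 participants per group with 80% power and alpha of 0.05". It then concludes: "Since there are three experimental groups in Study One, the total sample size would need to be higher than 42 participants". The Study Protocol section plans accordingly, "in three groups of 15 patients with vocal fold nodules", which is 45 patients, or 54 with the dropout allowance.

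The available text does not say whether Day, Group or Group x Day was powered. It gives no between-day correlation and no sphericity correction, and it states no detectable effect at 15 per group.

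**The concern.** Eta-squared 0.70 means that the effect explains 70% of the relevant variance. An effect that large should be detectable with a handful of patients per group, so 14 per group for only 80% power looks far too many. Either the effect size, the power or the test described is not the one used in the calculation.

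The direction is safe for the stated effect. What is at stake is interpretation. The Group x Day interaction carries the trial's hypothesis that sparser or summarised feedback gives poorer initial performance but better retention. If that interaction is not significant, the plan as written suggests a trial sized to detect only enormous effects, whereas its real sensitivity is much better and is not reported.

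**Working it through.** **Inputs from the SAP:** eta-squared 0.70, power 80%, alpha 0.05, k = 3 groups, m = 4 days. From the Study Protocol section: 15 per group planned.

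**Assumed, because the documents give no values:** between-day correlation rho from 0 to 0.8, and sphericity epsilon from 1 down to its floor for four days, 1/(m − 1) = 1/3.

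**Effect size.** f² = 0.70/0.30 = 2.333, so f = 1.528. Power comes from the noncentral F distribution with N = 3n.

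**1. Trying to reproduce 14 per group**

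*One-way, three groups:* lambda = f²N, df = 2 and N − 3.
- n = 2: 49.2%.
- n = 3: lambda = 2.333 × 9 = 21.0, power 88.5%.
- n = 4: 98.2%.
- n = 14: lambda = 2.333 × 42 = 98, power above 99.99%.

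*Group x Day in the mixed ANOVA:* df = 6·eps and 3(N − 3)·eps. The noncentrality depends on how the effect size is defined, so three conventions were used.

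| Convention | Smallest n per group for 80% power |
|---|---|
| lambda = f²·N·m·eps/(1 − rho) | 2–3 |
| lambda = f²·df2 (partial eta-squared) | 3–4 (n = 4 at eps 1/3: 93.8%) |
| lambda = f²·N·eps | 3, 4, 5, 6 at eps 1, 0.75, 0.5, 1/3 |

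The most demanding cell is the last convention at eps 1/3. With n = 6, lambda = 2.333 × 18/3 = 14.0, df = 2 and 15, power 86.5%. With n = 14, lambda = 2.333 × 42/3 = 32.7, df = 2 and 39, power 99.93%.

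*Group main effect over repeated days:* lambda = f²·N·m/(1 + 3·rho) gives 2–3 per group. The Day effect needs 2.

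No F test returns 14.

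**2. Working back from 14.** The eta-squared for which 14 is the smallest sufficient n is 0.199–0.212 one-way, and 0.427–0.446 under the most demanding interaction convention. Neither is near 0.70, and neither shows what the sponsor used.

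**3. What 15 per group can detect with 80% power**

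| Test | Detectable effect |
|---|---|
| Three groups on one day | f = 0.48 (eta-squared 0.19) |
| Group x Day, first convention, eps 1, rho 0 / 0.5 / 0.8 | f = 0.28 / 0.20 / 0.13 |
| Same, eps 1/3 | f = 0.42 / 0.29 / 0.19 |
| Group x Day, partial eta-squared, eps 1 to 1/3 | 0.10 to 0.20 |
| Group x Day, lambda = f²·N·eps, eps 1 to 1/3 | f = 0.56 to 0.83 |
| Two groups, two-sample t test | 1.06 SD; 1.25 SD with Bonferroni over three pairs |

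The f values in different rows rest on different definitions and should not be compared with one another.

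**The case against.** **The range of 2 to 6 covers omnibus F tests only.** The SAP also plans post hoc tests, and the hypothesis compares particular groups. If three equally spaced group means give eta-squared 0.70, adjacent groups differ by 1.528 × √1.5 = 1.87 SD. A two-sample t test then needs 6 per group unadjusted, 8 with Bonferroni over 3 tests, 11 over 18 and 12 over 36. On this reading, 14 per group corresponds to an eta-squared of about 0.46 unadjusted, 0.54 over 3 tests and 0.64 over 18. This point stands to the extent that 0.45 is a ceiling for the F tests and not for every conceivable test. It does not rescue the statement: the plan specifies neither that pattern of means nor any such adjustment, and even 36 tests do not reach 14.

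**Reading 0.70 as another statistic can come close.** Taken as d (f = 0.35), it gives 14 or 15 in some interaction forms; taken as f², it gives 15 in the most demanding one. Both contradict the plan's explicit eta-squared.

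**The sample-size text stops without a full stop, so more may have followed.** That weakens any claim that assumptions were never stated. The sentence giving 14 per group is complete, however, and can be checked as it stands.

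**The consequence is small.** These are described as preliminary studies, the sample exceeds what the stated inputs require, and a null result would also be read from its estimates and intervals. All true. That argues for leaving the sample alone, not for leaving an incorrect power figure in the plan.

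**Conclusion.** The concern holds. At eta-squared 0.70, 80% power and alpha 0.05, the F tests the plan describes need 2 to 6 patients per group, against 14 stated; 14 per group gives at least 99.93% power, against 80% stated. The interaction results rest on assumed correlations of 0 to 0.8 and epsilon of 1 to 1/3, but the conclusion does not depend on where in those ranges the truth lies. The one-way result needs neither assumption.

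The trial is not underpowered for the effect it names, and patients and procedures are unaffected. The fault is that the only justification for the sample size does not follow from its inputs, and the sensitivity of the trial at 15 per group is not reported in the available text. It should be corrected, but it is not critical.

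**What to change.** Keep 15 completers per group. In the sample-size paragraph of the Statistical Analysis Plan, delete the claim that 14 per group follows from eta-squared 0.70. Replace it with a statement that gives:

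- the test powered (Group x Day is the natural choice, as a named finding of interest);
- the effect-size definition, including whether eta-squared is partial;
- the between-day correlation and sphericity correction assumed;
- the effect detectable with 80% power at 15 completers per group under those assumptions.

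If the assumptions behind the sponsor's calculation are on file and do yield 14, state them instead, with the effect size actually entered.

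The cost is SAP wording only: no extra patients, and no change to procedures or tests.
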